- b. The VBA site with fact sheets about the different types of benefits available to Veterans. The topics covered in these fact sheets are: General Benefit Information, Veterans with Service-Connected Disabilities, Veterans with Limited Income, Education and Training for Veterans, Home Loans, Dependents and Survivors' Benefits, Burial and Memorial Benefits, and Insurance.
- c. The VBA websites for the local C&P office where issues pertaining to an individual Veteran's specific application are addressed. The site includes phone numbers to call with questions, e-mail contacts and directions to the VBA office.

3. Role of Therapists in Control Condition: The therapists in the control condition will differ from the Benefits Counseling therapist as shown in the table below

Control Therapist	Benefits Counseling Therapist
Initiate calls to Veterans at weeks 1 and 2	Initiate calls to Veteran at weeks 1 and 2 and around time of Module Three (or thereafter)
Up to three therapy calls of up to 30 minutes each	Up to three therapy calls of up to 30 minutes each
Convey information about Veterans Benefits	Convey information about Veterans Benefits AND vocational issues
Offer to elaborate on information on control websites	Inquiry about modules on Benefits Counseling website. Follow-up inquiries about domains covered on site.

Justification of Sample Size

We estimate that 190 Veterans will be enrolled and complete baseline assessments; 130 will log-in to the randomization site and be assigned to a treatment condition; 104 (52 per condition) will complete at least one follow-up assessment.

Precision Analysis

Consistent with the purpose of a pilot study, the sample size was selected to

estimate the standardized effect of treatment with reasonable precision, rather than to power for a statistically significant effect [50]; A **sample size of 52 per treatment condition** permits estimation of an expected standardized difference in slopes of hours worked between Benefits Counseling and control groups (e.g., (slopeBC-slopeCON)/SDslope) of $\delta=.40$ with a 95% confidence interval of (.01, .79). This effect would reflect an average 6% increase in baseline number of hours worked per month, or a total increase of 43% by month 6. Assuming an average baseline event rate of 40 hours/28 days and no change in the control group, this effect is equivalent to approximately 17 additional hours (approximately 2 days) of work per month by month 6.

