(i.e. going to the website for randomization vs. not doing so; using the Benefits Counseling website if assigned to it vs. not following the assignment). Potential predictors will be screened for their intercorrelations with each other and redundant measures will be pared or combined. We will then use bivariate analyses (t-test, chi-square) to identify factors that differentiate the groups of interest at a significance level of alpha = .10 or less. Identified factors will be entered into a logistic regression with group as the dependent variable (e.g. randomized vs. not). Factors to be considered include internet-associated factors (ease of internet access, extent of internet use), disability related factors (knowledge of disability process, desire to learn more about it), work-related factors (e.g. distress about not working), and demographic variables (age, gender, race, education status), and conditions that make internet use more difficult (e.g. BSI global severity).

Human Subjects

A. Consent Procedures

1. Recruitment: A waiver of informed consent and HIPAA authorization will be obtained to review the Compensation and Pension materials and charts of Veterans scheduled for Compensation and Pension examinations to identify those who are not more than 30% service-connected for physical conditions and scheduled for examinations for a psychiatric condition. The waiver will allow for the collection of basic demographic information concerning Veterans screened for study participation to determine if Veterans who consent to study participation differ systematically from those who do not.

The recruitment strategy involved identifying Veterans who have submitted requests for mental health Compensation examinations. Potentially eligible Veterans will be Express Mailed a letter from the P.I. explaining the basics of the study and that unless the Veteran opts out, a member of the research team will call to further explain the study. The letter will include a phone

number to call to opt not to receive the research call. No phone calls will be made to Veterans calling to opt out.

At that call, the Research Assistant will explain the study and invite the Veteran for a face-to-face meeting with further screening, informed consent, and baseline assessments. A Waiver of written informed consent will be obtained to screen potential participants over the phone.

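### Predictors of log-on and website use are screened at alpha .10 and then estimated on the same Veterans, so the reported odds ratios will be too large and their intervals too narrow

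*Combined protocol and SAP*

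**What the plan says.** Item 7 of the Data Analysis section covers two outcomes: whether an enrolled Veteran goes to the website to be randomized, and whether a Veteran assigned to Benefits Counseling uses its website.

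The steps are:
- **Paring.** "Potential predictors will be screened for their intercorrelations with each other and redundant measures will be pared or combined".
- **Screening.** Each remaining factor is tested alone, by t-test or chi-square, "to identify factors that differentiate the groups of interest at a significance level of alpha = .10 or less".
- **Refitting.** The next step reads: "Identified factors will be entered into a logistic regression with group as the dependent variable (e.g. randomized vs. not").

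The candidates are two internet factors (access and amount of use), two on the claims process (what the Veteran knows and wants to know), one work factor (distress over being out of work), four demographic ones, and one under the label "conditions that make internet use more difficult (e.g. BSI global severity"). That is 2 + 2 + 1 + 4 + 1 = 10 named factors, two of them given only as examples.

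The section on sample size supplies the denominators: "We estimate that 190 Veterans will be enrolled and complete baseline assessments; 130 will log-in to the randomization site". Item 7 gives no significance level for the logistic model, no multiplicity adjustment, no correction or validation for selecting and estimating on the same data, and no statement that the results are hypothesis-generating.

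**The concern.** A factor reaches the logistic model only if its observed association was large enough to pass the screen, and the model then re-estimates that association from the same observations. Small estimates are removed before anything is reported. Those that remain are too large on average, and the ordinary standard errors take no account of the selection.

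What is at stake is the description of who is lost before randomization. The Study Design Overview randomizes only after log-on, in order to keep Veterans with some motivation and web access, and 190 − 130 = 60 are expected to fall out there. Item 7 is the planned account of how they differ, and so of whom the trial result describes. Inflated odds ratios with narrow intervals would make that account look firmer than the data allow.

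**Working it through.** The plan states no error rate or interval for this analysis, so there is no figure of its own to reproduce.

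**Inputs from the documents.** Screening alpha .10; ten named factors; 190 enrolled, 130 randomized, 60 not.

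**Assumptions.** Two-sided tests. Standardised factors. Final level .05, because none is stated. About 130/2 = 65 Veterans assigned to Benefits Counseling, with 13 to 20 non-users. Correlations between factors from 0 to .5.

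**1. Interval coverage for a null survivor, by hand.** If screen and refit give nearly the same test, a null factor passes with probability .10 and has p<.05 with probability .05. Among survivors, .05/.10 = 50% have a 95% interval that excludes the true value, so coverage is about 50%. Simulation of the full two-stage procedure gives 54–59% with independent factors and 75–78% at r=.3, subject to a few points of simulation error.

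**2. Size of a null survivor's odds ratio, by hand.** The screen requires |z| > 1.645. The mean |z| of null survivors is φ(1.645)/.05 = .1031/.05 = 2.06. The standard error of a log odds ratio per SD is about √(n/(n₁n₀)).

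| Analysis | Standard error | exp(2.06 × SE) | Simulated, independent factors |
|---|---|---|---|
| 130 vs 60 | √(190/7800) = .156 | 1.38 | 1.39 |
| 45 vs 20 | √(65/900) = .269 | 1.74 | 1.83 |
| 52 vs 13 | √(65/676) = .310 | 1.89 | 2.04 |

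The simulated values are exp(mean |log OR|). The true value in every row is 1.

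**3. A factor with a real effect.** Take a true odds ratio of 1.36 per SD in the log-on analysis. Then log 1.36 = .307 and .307/.156 = 1.97. The factor passes with probability P(Z > 1.645 − 1.97) = .63. Given that it passes, the mean z is 1.97 + φ(.325)/.63 = 1.97 + .378/.63 = 2.57, and exp(2.57 × .156) = 1.49. Simulation gives about 1.5 at n=190 and 2.0–2.1 at n=65. One Firth model with all factors gives about 1.36, with 96–97% interval coverage across all factors.

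**4. Multiplicity, a separate matter.** For ten independent null factors, 1 − .90¹⁰ = 65.1% is the chance that at least one passes the screen, and 1 − .95¹⁰ = 40.1% is the chance of at least one p<.05. Simulated rates of at least one final p<.05:

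| Setting | Independent | r=.3 | r=.5 |
|---|---|---|---|
| Screened, n=190, 10 factors | 37–38% | 22–24% | 13% |
| Screened, n=65, 10 factors | 30–35% | 20–22% | – |
| Screened, n=190, 8 factors | 31% | 21% | – |
| Screened, n=190, 12 factors | 41% | 27% | – |

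The range is thus roughly 13–41%. It is higher if the final model is read at .10 (34–64% for ten factors at n=190). For comparison, one unscreened ten-factor logistic model at .05 gives 40–44%, and a Firth model with all ten gives 22–33%.

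**5. Does paring help?** Item 6 (moderators) gives r > .7 as an example of redundancy. Paring at that level removes near-duplicates. It leaves several distinct tests, and it does nothing about estimating a factor on the data that selected it.

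**The case against.** A reader might infer that the .10 screen itself produces a false predictor in about a third of analyses. The documents do not support that. The plan never sets .05, or any level, for the final model, so the figure is not a property of the plan. It falls to 20–24% for ten factors at r=.3 and to 13% at r=.5. Entering all ten factors unscreened gives 40–44%, which is no better and usually worse. The false-positive rate is ordinary multiplicity over about ten factors, and dropping the screen alone would not lower it.

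Inflation is also not peculiar to a screen. Reporting only the significant factors from an unscreened model selects on the same data too. A full model therefore helps only if every factor is reported.

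The analysis is ancillary as well. It is in neither the primary nor the exploratory aims, no decision rule depends on it, and the trial is presented as a pilot sized for precision. All of this stands and limits the weight of the point.

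It does not answer the estimation problem. The plan makes the .10 filter a formal step, corrects nothing afterwards, and does not say that the results are exploratory. Sizing a pilot for precision is a reason to report estimates with honest intervals rather than to filter them by significance.

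**Conclusion.** The point holds as one about biased estimates and misleading intervals after selection. With ten independent standardised factors, null survivors carry odds ratios per SD of about 1.4 (n=190) or 1.8–2.0 (n=65). Their nominal 95% intervals cover 54–59%, or 75–78% at r=.3. A true odds ratio near 1.36 is reported as about 1.5 or 2.0–2.1. These sizes rest on the assumed number of factors, correlations and user split. The direction of the bias does not.

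The lack of multiplicity control is a second, separate gap, worth roughly 13–41% at an assumed final level of .05. It should not be attributed to the screen.

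The importance is minor. Claims about who logs on or uses the site are affected; the treatment comparison is not.

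**What to change.** - **Log-on analysis (190 Veterans).** After redundancy paring, replace the .10 screen with one pre-specified Firth-penalized logistic model containing all listed factors. Report every factor's odds ratio and confidence interval, significant or not.
- **Website-use analysis (about 65 Veterans).** Report all unadjusted odds ratios with confidence intervals, as descriptive only. With 13 to 20 non-users and ten factors there would be 1.3 to 2 non-users per coefficient, too few for an adjusted model to be relied on.
- **Both.** Label item 7 hypothesis-generating, or name a multiplicity adjustment if p-values are to be used to declare predictors. Firth penalization does not supply one.

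The cost is a change of wording in the analysis plan, with no new data. The price is wider intervals and more modest odds ratios.

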2. Becoming upset while discussing traumatic events: There is a risk that individual Veterans will become upset by discussing their traumatic events during assessments or counseling. In practice, study-related adverse events in clinical trials involving PTSD assessments among Veterans have been very rare. Research assistants will emphasize that answering questions is voluntary and will allow Veterans to answer questions at their own pace and without duress.

3. Information from the counseling being told to participants' clinicians at the VA or to someone who reviews their disability application. The counseling is unlikely to impact the Veteran's disability application. The therapist will not volunteer any non-emergent information in the Veterans' chart or to other clinicians, as this is contrary to the voluntary, Motivational Interviewing stance that is integral to Benefits Counseling. The therapist will write a note in the Veteran's VA chart after any phone counseling indicating that the participant was in this research study and spoke to the therapist.

Nevertheless, the therapist is going to convey information to other VA clinicians if the Veteran indicates information during the therapy that requires emergency intervention. If the Veteran indicates information suggesting imminent danger to the Veteran or to others, the Benefits Counseling therapist will share this information with other VA clinicians so they can take appropriate action. Therefore, Veterans will be told the risk that information that they tell the study therapist may be told to their VA clinicians and would then become available to someone who reviews their disability application. It is very unlikely that an emergency disclosure would prevent receipt of service-connected disability.

4. Potential effect of work on the benefits application process: Veterans compensated for physical or mental problems that developed during or were made worse by military service are not supposed to be penalized for coping well with these problems by working. However, the Veterans Benefits Administration reviews claims on a case-by-case basis, and it is unknown to what extent working will influence any individual Veteran's disability determination process. Veterans will be told this as part of the informed consent process.

5. Breach of Confidentiality: The website will not contain any PHI.

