However, the Veterans' computer that accesses the website will leave a trace (in the history of browsed sites on the local computer). Therefore, if a subsequent user of a computer knows the specific Veteran who used an account, the user may infer that the Veteran has a Compensation claim and/or a psychiatric disorder.

Research Assistants and Therapists will clarify communication procedures with Veterans. They will ask the Veteran's preference in terms of whether or not the Veteran wants messages left on voicemail, and if so, if the Veteran wants the study therapist's phone number left on the voicemail. Therapists will establish that the Veteran is the person answering the phone by using personal identifiers drawn from a standard list of security questions (mother's maiden name, etc.) that the Veteran has supplied.

C. Protection of Participants

1. Confidentiality of Research Materials: All research information is considered confidential. All computers used by research staff are password protected. Limits to confidentiality include only disclosure of acute suicidality, homicidality, or abuse of a minor, as is standard in clinical practice. If a Veteran selects any value over 1 ("a little bit") on the Brief Symptom Inventory question about "thoughts about ending your own life," the Research Assistant will contact [name], his covering psychiatrist or, if neither is available, the clinician handling intakes to arrange for an evaluation of the Veteran.

All screening forms will have a study code number but no identifying information. Electronic files containing identifiable information will be kept on a secure VA server available only to research staff.

Research data will be identified by code number and will not include names, although enrollment records must also be kept and these records will include names. Our study forms have

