4. Training of Study Therapists: The risk of angering or alienating Veterans is very small because of the non-confrontational nature of Benefits Counseling. The risk will be further minimized by hiring staff who have experience with the study population. Study therapists will be trained to adopt a collaborative approach. Study therapists will also be taught the phone numbers to call in case of an emergency during a telephone call with Veterans.

5. Training of Research Assistants: Research Assistants will also be taught where the emergency facilities are including the location of emergency rooms, VA and public police and crisis services. Research Assistants will also receive training in de-escalating agitated Veterans.

D. Data Safety Monitoring Plan:

1. Data Management Plan

Careful training of evaluators will precede study initiation. The main instrument on which training is needed is the baseline Work-Related Activities timeline-follow-back calendar. Training to conduct the Work-Related Activities Calendars will involve at least three supervised ratings.

Our research group will be using REDcap, a free, secure VA Web application that allows for the collection and entry of research data. In addition to enabling users to develop surveys and databases without additional software, REDcap helps researchers enter, store and manage project data. All data entries will have a study code number but no identifying information. Registration records including the signed consent form will be stored separately from these study records.

2. Safety Monitoring Plan: The risk to Veterans who do go on to be randomized to Benefits Counseling or Control is low (greater than minimal). Veterans presenting with PTSD symptoms and other psychiatric conditions for Compensation and Pension examinations have a high frequency of medical and psychiatric difficulties. Therefore, changes in medication regimen, the presence of medication side effects and symptom exacerbations are not untoward and do not constitute adverse events. Anticipated adverse events include complaints about the study procedures and the counseling, and any occurrence in which the patient attributes discomfort, harm or disability to the study procedures.

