In the clinical trial, assessment for adverse events will be a routine part of every study and therapy visit. Any report that a patient required overnight treatment in any facility (emergency room, detoxification, and hospitalization) will constitute an SAE, as will any report of death or serious disability. Hospitalization or death of another individual due to direct action of patient will also be considered an SAE.

Any SAEs will be immediately reported to [name] and, if he is unavailable, to [name]. Reports to [name] will include a description of the event and a summary of recent contacts with the patient. This summary will include any warning signs of the adverse event, the patient's general state and any information suggesting a causal link between study participation and the event. [name] will report these to the IRB within 3 working days.

The New England MIRECC's D.S.M.B. will be the D.S.M.B. for this study. The D.S.M.B. will be contacted within 3 days about all significant study-related adverse events. The main risks of the study are frustration with the study procedures, frustration with the Benefits Counseling website, and someone learning about the Veteran accessing the Benefits Counseling website without the Veteran's permission. Because of the very low risk that either therapy would worsen outcomes, no a priori stopping criteria are proposed. Every year, [name] and the D.S.M.B. will review study information on a standardized form. Board members will review recruitment, retention, and follow-up rates for the study-to-date, SAEs and AEs and other data as the D.S.M.B. deems necessary.

Based on this report, each DSMB member will complete a form making one of two recommendations: 1) continue recruitment as planned; or 2) schedule formal DSMB meeting immediately. If any DSMB member recommends a meeting, this will be scheduled within one week, minutes will be kept, the report will be reviewed with the PI, and the committee will vote on whether the study should: 1) continue recruitment unchanged; 2) continue with a protocol amendment; 3) stop recruiting pending further investigation. If, after this meeting, any DSMB member votes to stop recruitment or requests a protocol modification, the Yale IRB will be informed.

A written summary including this information will be provided to the IRB with the protocol renewal.

D. Potential Benefits

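### The blanket exclusion of symptom exacerbations from adverse events conflicts with the adjacent AE and SAE rules, and a suicide attempt without an overnight stay has no required reporting route

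*Combined protocol and SAP*

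**What the plan says.** The rules are spread over three parts of the Human Subjects section.

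- **Data Safety Monitoring Plan, 2. Safety Monitoring Plan (AEs).** Applicants with PTSD and other psychiatric conditions are said to "have a high frequency of medical and psychiatric difficulties". From this the plan concludes that "changes in medication regimen, the presence of medication side effects and symptom exacerbations are not untoward and do not constitute adverse events". The next sentence lists anticipated AEs, among them "any occurrence in which the patient attributes discomfort, harm or disability to the study procedures".
- **Same section (SAEs).** "Any report that a patient required overnight treatment in any facility (emergency room, detoxification, and hospitalization) will constitute an SAE". The list also covers the participant's death or serious disability, and hospitalization or death of another person caused directly by the participant.
- **Same section (routes).** AEs are asked about at every study and therapy visit. SAEs go to the IRB within 3 working days. The DSMB is contacted within 3 days about AEs that are both significant and study-related; the first term is not defined. Each year it reviews SAEs, AEs and any other data it thinks necessary. There are no stopping criteria.
- **B. Risks and Discomforts, items 2 and 3.** "There is a risk that individual Veterans will become upset by discussing their traumatic events during assessments or counseling". If a Veteran discloses imminent danger to self or others, the therapist tells VA clinicians.
- **C. Protection of Participants, 1. Confidentiality of Research Materials.** "If a Veteran selects any value over 1" on the Brief Symptom Inventory item about ending one's own life, the Research Assistant arranges a clinical evaluation. The section does not say whether this is recorded as an event.

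**The concern.** The reason given for the exclusion is a high background rate of symptoms. That is a fair reason not to log every fluctuation. The sentence goes further, because it covers every exacerbation, including one that the Veteran blames on the trauma questions or that ends in an overnight stay. Staff who follow it literally would leave out events that the neighbouring sentences require them to count.

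The SAE list also turns on where and how long the participant was treated, and on outcome. A suicide attempt that is treated and released the same day, with no lasting disability, meets none of its criteria. The two places where the study would most readily learn of suicide risk lead to clinical action but to no stated study record.

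At stake is whether the DSMB reliably receives these events. With no stopping criteria, its yearly review of AEs and SAEs is the main safety check in the plan. When background events are frequent, attribution of a single case is weak, and a comparison of counts between arms is more informative. That comparison needs the events to be recorded under one consistent rule.

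**Working it through.** No arithmetic applies. The plan gives no event rates, and the point depends on definitions. The check takes six event types and applies the written AE, SAE and reporting rules to each.

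1. **Exacerbation, not attributed to the study, no SAE criterion met.** The exclusion makes it a non-AE, and no other rule includes it. The classification is clear and matches the stated rationale.
2. **Exacerbation the Veteran attributes to study procedures, no overnight stay.** The exclusion says "symptom exacerbations are not untoward and do not constitute adverse events". The next sentence counts "any occurrence in which the patient attributes discomfort, harm or disability to the study procedures". Nothing says which governs. This is the risk described in item 2 of Risks and Discomforts. Contradictory.
3. **Exacerbation with overnight treatment.** The SAE rule captures it without any attribution test, so it goes to the IRB within 3 working days and into the yearly DSMB review. The exclusion says that an exacerbation is not an AE at all. Contradictory, although the specific SAE rule would probably prevail in practice.
4. **Suicide attempt without overnight stay, death or serious disability, and no harm to another person.** No SAE criterion is met. It is an AE only if the Veteran attributes it to the study, or if staff use the open-ended wording of the anticipated-AE list. If staff class it as an exacerbation, the exclusion applies. No required route.
5. **Suicide attempt with overnight stay, death or serious disability.** SAE. Clear.
6. **Suicide-item trigger after baseline, or disclosure of imminent danger.** Clinical action is specified. No sentence makes either one an AE, an SAE or an item for the DSMB. No required route.

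Result: types 1 and 5 are clear, types 2 and 3 are contradictory, and types 4 and 6 have no required route.

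The inventory is administered at baseline and at weeks 4, 12 and 24 (Schedule of Assessments), so type 6 can arise at three follow-ups per Veteran. How often it would arise cannot be derived from the documents.

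**The case against.** The strongest reply is that the two AE sentences can be read together. The exclusion follows from the population's background rate, so it naturally means background exacerbations. The next sentence then brings back anything attributed to the study. That sentence is also an open-ended list of anticipated AEs and not a full definition, so staff are free to record a suicide attempt. No sentence classes an attempt as a symptom exacerbation. This reading is sensible and probably the intended one, but the text does not state it, and staff apply the text. The reply narrows the conflict to attributed and overnight exacerbations without removing it. It leaves the recording of type 4 to discretion.

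Three stronger readings are tempting, and the documents do not support them.

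- A reader might infer that psychiatric harms need never reach the DSMB. They can: overnight treatment, death and serious disability are SAEs regardless of cause, AEs are asked about at every visit, and the board sees both yearly and may ask for more.
- A reader might infer that the definitions remove the data needed to judge whether either therapy worsens symptoms. They do not. The Brief Symptom Inventory and PTSD Checklist are collected in both arms at baseline and at all three follow-ups, whatever counts as an AE.
- A reader might infer that these are the most likely harms. The plan names frustration and loss of privacy as its main risks, and describes study-related events in trials with PTSD assessments as very rare.

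**Conclusion.** The point stands in limited form. The exclusion conflicts with the sentence after it for attributed exacerbations, and with the SAE rule for exacerbations with an overnight stay. The SAE list does not reach a suicide attempt without an overnight stay, death or serious disability. Suicide-item triggers and imminent-danger disclosures have no stated link to AE recording. Such events reach the DSMB only if staff record them as AEs or the board asks for them.

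This is more than missing detail, because a written rule, followed literally, leaves a serious event outside required reporting. It should be corrected, but it does not show that the trial is unsafe.

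The size is stated by event type: four of the six types tested are contradictory or lack a required route. A number of missed events would need an assumed endorsement rate for the suicide item, for which the documents offer no basis. It would also count screening triggers and not harms, and one Veteran could contribute several. The conclusion needs no such figure. It assumes only that the rules are applied as written and that the yearly DSMB form, which is not reproduced, does not already ask for these events.

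**What to change.** Reconcile the Safety Monitoring Plan with Risks and Discomforts (items 2 and 3) and Confidentiality of Research Materials:

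1. Limit the exclusion to background exacerbations that the Veteran does not attribute to the study and that meet no SAE criterion.
2. State that any suicide attempt is a reportable event, with or without an overnight stay.
3. State how an imminent-danger disclosure is to be recorded.
4. Log each post-baseline suicide-item trigger, so that counts by arm are available on the existing yearly DSMB form. Count Veterans as well as triggers, since one Veteran can trigger at weeks 4, 12 and 24. The counts by arm should be compiled by someone other than the blinded Research Assistant.

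This changes reporting only. Clinical evaluation, disclosure to clinicians and the absence of stopping criteria stay as written. Yearly symptom means by arm for the DSMB are not needed to close the gap and are not requested here; they would add repeated looks at trial outcomes without a rule for interpreting them.

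The cost is a wording amendment, a line or two on the form, and a modest increase in logged events in a population where symptoms are frequent.
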